## **ORGANIZATION OF DETAILED PROTOCOL**

**Title:** Effects of Transcranial Direct Current Stimulation (tDCS) and Transcranial Ultrasound (TUS) on the perception of pain and functional limitations due to Non-Specific Chronic Low Back Pain (NSCLBP) (phase II)

### **Sponsors**

This study is funded by the NIH NIA and conducted in conjunction with Highland Instruments (co-applicant in this grant proposal). Highland Instruments is a company focused on developing neurostimulation technologies for treatment of neural pathologies.

## **II. SUBJECT SELECTION**

In phase II, we will recruit about 80 subjects in order to randomize 40 patients with NSCLBP for this study. Subjects will need to meet all of the following inclusion criteria and none of the following exclusion criteria:

Inclusion Criteria:

1. Providing informed consent to participate in the study
2. 18 to 85 years old
3. Having non-specific chronic low back pain as defined by [6, 7] (existing pain for at least 3 months and having pain on at least half the days in the past 6 months) with an average of at least 3 on a 0-10 VAS scale
4. Pain resistant (partial or no response) to common analgesics and medications for chronic pain such as Tylenol, Aspirin, Ibuprofen, Soma, Parafon Forte DCS, Zanaflex, and Codeine
5. Must have the ability to feel sensation by Von-Frey fiber on the forearm

Exclusion Criteria:

1. Subject is pregnant
2. Contraindications to tDCS in conjunction with TUS:
  - a. Metallic implant in the brain
  - b. Implanted brain medical devices
3. History of alcohol or drug abuse within the past 6 months as self reported
4. Use of carbamazepine within the past 6 months as self reported
5. Suffering from severe depression (with a score of >30 in the Beck Depression Inventory)
6. History of neurological disorders as self reported (including epilepsy (note patients will also be evaluated via EEG at baseline and any patient showing abnormal EEG activity will be removed))
7. History of unexplained fainting spells as self reported
8. History of severe head injury resulting in more than a momentary loss of consciousness as self reported
9. History of neurosurgery as self reported
10. Unstable pain (defined as a difference in pain intensities larger than 4 points on a 0-10 VAS scale between the average over the week prior to visit 2 and the average over the week prior to visit 4a [96])
11. Large placebo responder: having a reduction of pain greater than 72.52% (VAS pain now post stimulation on V3 compared with VAS pain now pre stimulation on V2) or VAS now of 0 or 1 following any stimulation during Run-in period.
12. Low Adherence during the Run-in stimulation visits (ie. not attending both Run-in stimulation visits within approximately one week)
13. Low baseline pain: VAS pain weighted average < 3 prior to randomization during visit 4a

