### **III. STUDY PROCEDURES**

Because our protocol involves a run-in phase (Part I), we expect that up to 90 patients may enter the run-in phase so we will be able to randomize 40 eligible subjects to participate in this study (in phase II). When the target number of 40 subjects (for phase II) entering the randomized phase

(Part II) is completed, enrollment will end. Subjects who passed the run-in phase (Part I) successfully will then be randomly assigned to receive treatment in Part II with active tDCS+active TUS (n=20) or sham tDCS+sham TUS (n=20 inactive transducers).

**General Study Outline:** This two-Part study will consist of 23 visits over the course of about 15 weeks. After Visit 1, the remaining Part I of the study will take about a week (Visits 2-4a). Prior to any assessments, the subject will consent to participate in both Part I and Part II, pending that the subject fits the additional eligibility criteria\* of the run-in period. After completion of Part I, eligible subjects will continue onto Part II, the main interventional portion of the trial. Part II of the study will take place over the remaining weeks (Visits 4b-23).

*Part I Study Flow – Run-in Period (Visits 1-4a):*

- Screening Visit
- Run-in Visit 2&3 – sham stimulation visits
- Rescreening Visit

*Part II Study Flow – (Visits 4b-23):*

- 10 sessions of tDCS stimulation over 2 weeks
- Bi-weekly sessions of tDCS stimulation over 3 weeks
- 4 Follow-Up Visits – 2 week, 4 weeks, 6 weeks, and 8 weeks post-stimulation

Eligibility criteria for Part II include:

- VAS pain score greater than 1 following either of the two SHAM stimulation sessions [97] during Part I and pain reduction not greater than 72.52% (i.e. not a large placebo response)
- Stable pain intensities (defined as a difference in pain intensities less than or equal to 4 (on a 0-10 VAS scale) between the average over the week prior to visit 2 and the average over the week prior to visit 4a [96])
- High adherence during the Run-in stimulation visits (defined as completing both Run-in stimulation visits within approximately one week)
- VAS pain weighted average  $\geq 3$  prior to randomization during visit 4a (i.e. not exhibiting low baseline pain)

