### **Visit 4a**

Rescreening Visit – (Approx Time: 1 ¼ hours)

*This study will be scheduled ~1 week after the first baseline measurements were done.*

The subject will complete a series of assessments:

- Urine pregnancy exam (if applicable)
- Visual Analog Mood Scale (VAMS)
- Mini Mental State Examination (MMSE)
- Stroop test
- Neurological and Physical Exam
- Visual Analogue Scale (VAS) for Pain
- Pain/Medication Diary
- Quantitative Sensory Testing (QST)
- Walking Test
- Postural Stability/Standing Test
- One Leg Stance Test
- Trunk Mobility Test
- Screening form for part II\*

\* If the subject is eligible for part II, then they will complete visit 4b in the same day.

Note, patients who exhibit large placebo effects (defined as exhibiting VAS=0 or VAS=1) following either of the two SHAM stimulation sessions[97] during Part I and score reduction higher than 72.52%; unstable pain intensities (defined as a difference in pain intensities larger than 4 (on a 0-10 VAS scale) between the average over the week prior to visit 2 and the average over the week prior to visit 4 [96]), low baseline pain (defined as weighted VAS avg < 3) prior to randomization during visit 4) or who are not compliant with the Run-In protocol (defined as not completing both Run-in stimulation visits within approximately one week) will be excluded from the full trial [96-98], and thus will not receive MRIs and will not come for

additional visits. By following this Run-in strategy, we will maximize trial resources by excluding patients who demonstrate poor compliance and are less likely to complete the trial. More importantly, we will increase the likelihood that the effects we are measuring in the full trial are biological in nature and directly caused by the stimulation intervention [97, 98]. Note, a patient can be screened out in any of the visits prior to Visit 4b.

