#### *Randomization:*

Once eligibility and consent have been approved and completed, after all baseline evaluations and immediately before the first stimulation session of Part II, stratified blocked randomization will occur using the randomized list generated by an automatic web-based randomization program ([www.randomization.com](http://www.randomization.com)). Randomization will be based on placebo effect above or below -17.3% according to preliminary data. A staff member who is not involved in any of the study procedures will be responsible for creating the randomization list and monitoring it during the study. Subjects will be randomly assigned to treatment or placebo groups in a 1:1 allocation ratio. We will use permuted blocks of variable sizes (4) in a random manner to minimize the risk of study staff guessing at the next allocation. Randomization order will be kept in sealed envelopes.

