#### **IV. BIOSTATISTICAL ANALYSIS**

Data forms and questionnaires will be coded in a standardized manner, and double-entered into our database. Digital measures/recordings will be similarly tracked in our database and regularly backed up. Analyses will be conducted using standard statistical software such as SAS and Matlab.

Sample size calculations and data analysis:

*Aim 1:*

For planning sample size calculation for this study, we considered the surrogate pain outcomes as the main outcome for such analysis; considering the two studies showing significant alterations of these outcomes in NSCLBP [118], an effect in the active tDCS in conjunction with active TUS that is twice of the effect in SHAM tDCS in conjunction with SHAM TUS would be adequate. Considering this effect size and a power of 80% and alpha of 5%, we would need 6 subjects per group for a total of 12 subjects. Therefore considering dropouts and also to increase the sample in phase I for the clinical outcome, we increased the sample to 20 subjects (10 for each arm), that would also give a power to detect significant differences of 2 points in VAS between the 2 groups; though the clinical outcome is not the main outcome in phase 1. For Phase 2, we doubled the sample size as to have enough power to detect a difference of 1.3 in VAS between the two groups that would therefore be adequate to demonstrate a clinically meaningful difference between the two groups. We considered differences smaller than that not clinically meaningful.

All analyses will be conducted according to the principle of intention-to-treat (using regression-based single imputation method). We will also perform an additional sensitivity analysis in

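### The eligibility criteria do not exclude Phase I participants or others who have already had tDCS/TUS, so patients who may recognise active stimulation could enter a sham-controlled comparison with a self-reported outcome

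*Combined protocol and SAP*

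**What the plan says.** Section II (Subject Selection) states the entry rule as a closed list: "Subjects will need to meet all of the following inclusion criteria and none of the following exclusion criteria". Five inclusion and 13 exclusion criteria follow. The item "Contraindications to tDCS in conjunction with TUS" has two sub-items, metal in the brain and implanted brain devices. Past exposure to a drug is covered, "Use of carbamazepine within the past 6 months as self reported", but past exposure to the study intervention is not. The further Part II criteria in section III and at Visit 4a concern placebo response, stability of pain, run-in attendance and baseline pain only.

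Section IV (Biostatistical Analysis) describes a Phase I with the same active and sham combination, for which "we increased the sample to 20 subjects (10 for each arm". Phase II randomises 40, and for this "we expect that up to 90 patients may enter the run-in phase so we will be able to randomize 40 eligible subjects" (section III); section II speaks of recruiting about 80. The Randomization paragraph says "Subjects will be randomly assigned to treatment or placebo groups in a 1:1 allocation ratio" and "Randomization will be based on placebo effect above or below -17.3% according to preliminary data". Prior stimulation is not a stratification factor. The Blinding paragraph keeps patients blinded until their visits end and then offers sham patients open-label active treatment.

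**The concern.** The main Phase II outcome is VAS pain, which the description of assessments defines as self-reported. A patient who has felt active stimulation, or was told an earlier allocation, may recognise the Part II arm and report accordingly. Expectation would then lower reported pain in the active arm and raise it, or fail to lower it, in the sham arm. Randomisation balances how many such patients each arm holds. It does not cancel an effect that runs in opposite directions in the two arms.

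This matters for a plan that justifies its run-in by saying "More importantly, we will increase the likelihood that the effects we are measuring in the full trial are biological in nature". Nothing later would reveal the problem. No visit lists a check of whether patients guessed their arm, and the model adjusts for baseline variables that are not named.

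**Working it through.** **1. Is there a rule anywhere?** The places that could hold one are the section II criteria, the Part II criteria in section III, the pre-screening, Visit 1 and Visit 4a text, the Randomization and Blinding paragraphs, and section IV. None mentions earlier tDCS, TUS or Phase I participation. The phone questionnaire is named but its content is not reproduced. A question there would not in itself be an exclusion criterion.

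**2. The plan's own figure.** Phase II has 20 per arm, said to suffice for 1.3 VAS points. No SD is given, so this cannot be reproduced. Assuming a two-sided 5% t-test and 80% power, 20 per arm needs a standardised difference of 0.909, which implies SD = 1.3 / 0.909 = 1.43. The omission does not affect the sample size.

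**3. How many non-naive patients could be randomised?**
- Run-in yield from the documents: 40/90 = 44% to 40/80 = 50%.
- All 20 Phase I subjects return: 20 × 0.444 = 8.9 to 20 × 0.50 = 10.
- Only the 10 from the active arm count: 10 × 0.444 = 4.4 to 10 × 0.50 = 5.
- None return: 0.

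Applying the general yield to returning patients is an assumption.

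**4. Bias.** Let f be the non-naive share of the 40 and s the change in the active-sham difference among non-naive patients caused by knowing the arm. With f equal in both arms, the observed difference is (1 − f)δ + f(δ + s) = δ + f·s, so the bias is f·s. The documents give no value for s. The base assumption is 1 point, with 0.5 and 2 shown as a range.

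| Return scenario | Non-naive of 40 | s = 0.5 | s = 1 | s = 2 |
|---|---|---|---|---|
| None | 0 | 0 | 0 | 0 |
| Phase I active arm only | 4.4-5 | 0.06 | 0.11-0.125 | 0.22-0.25 |
| All Phase I | 8.9-10 | 0.11-0.125 | 0.22-0.25 | 0.44-0.50 |

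At s = 1, the all-return row is 17-19% of 1.3 points (0.222/1.3 and 0.25/1.3). The active-arm row is 9-10% (0.111/1.3 and 0.125/1.3).

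**5. Effect on the test.** With no true effect, SD 1.43 and a two-sided t-test at 20 per arm, the chance of a significant result rises from 5% to 8.4% with 10 of 40 non-naive and s = 1, and to 19% with s = 2. With 4 of 40 the figures are 5.5% and 7.2%. These are illustrations on assumed inputs.

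**The case against.** The strongest reply is that the route to harm is hypothetical. No section says that Phase I patients will be approached again or were told their allocation. Early unblinding and open-label treatment are described for the present study, and applying them to Phase I is an inference. Every randomised patient also has two sham sessions in the run-in, so naive patients too have a sham reference, and the extra effect of Phase I experience is unknown. All of this stands, and it limits what can be said about size. It does not supply the missing criterion, and a naive patient still lacks the experience of active stimulation.

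A reader might infer more than the documents support:

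- *Carry-over or return of known responders biases the comparison.* Inclusion 3 and exclusions 10 and 13 require frequent, stable pain averaging at least 3, which works against patients with marked residual benefit. The 1:1 allocation balances whatever remains, on average.
- *The run-in selects experienced patients because they do not respond to sham.* Nothing in the documents shows this. If it were so, such patients would tend to fall in one placebo-effect stratum and be balanced within it.
- *Half the trial could be non-naive.* Twenty of 40 would give 0.50 points, or 38% of 1.3, but only if every Phase I subject returned and every one passed the run-in. The plan itself expects 44-50% to pass.
- *Run-in failures might be rescreened.* No section provides for it, so it is not part of this point.

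**Conclusion.** The gap is real. Followed as written, section II admits Phase I participants and others with earlier tDCS/TUS to a sham-controlled comparison on a self-reported outcome. The consequence is possible rather than shown. The bias is zero if none return. With a 1-point expectation shift and the general run-in yield, it reaches about 0.22-0.25 points if all 20 Phase I subjects return, or about 0.11-0.125 if only those from the active arm count. A higher pass rate among returning patients would raise these figures, but the documents give no basis for one. Patients with earlier stimulation from other sources would add to the count, and their number is unknown. Confidence in the omission is high and in its size low. The case for acting is that the remedy is cheap and the resulting bias would be hard to detect or remove afterwards.

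**What to change.** Add one exclusion criterion to section II: previous participation in Phase I of this study or any open-label treatment linked to it, or previous tDCS or TUS. Check it at the phone screen and again at Visit 1.

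If the sponsor does not want to exclude all earlier tDCS/TUS from other sources, keep the Phase I exclusion, record other earlier stimulation at screening, and specify a sensitivity analysis in stimulation-naive patients.

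The cost is one criterion and one screening question. The planned 40 is unchanged. The downside is a small loss of recruitable patients: up to 20 from Phase I, plus any others with earlier stimulation if they too are excluded.

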### **III. STUDY PROCEDURES**

Because our protocol involves a run-in phase (Part I), we expect that up to 90 patients may enter the run-in phase so we will be able to randomize 40 eligible subjects to participate in this study (in phase II). When the target number of 40 subjects (for phase II) entering the randomized phase

(Part II) is completed, enrollment will end. Subjects who passed the run-in phase (Part I) successfully will then be randomly assigned to receive treatment in Part II with active tDCS+active TUS (n=20) or sham tDCS+sham TUS (n=20 inactive transducers).

**General Study Outline:** This two-Part study will consist of 23 visits over the course of about 15 weeks. After Visit 1, the remaining Part I of the study will take about a week (Visits 2-4a). Prior to any assessments, the subject will consent to participate in both Part I and Part II, pending that the subject fits the additional eligibility criteria\* of the run-in period. After completion of Part I, eligible subjects will continue onto Part II, the main interventional portion of the trial. Part II of the study will take place over the remaining weeks (Visits 4b-23).

*Part I Study Flow – Run-in Period (Visits 1-4a):*

- Screening Visit
- Run-in Visit 2&3 – sham stimulation visits
- Rescreening Visit

*Part II Study Flow – (Visits 4b-23):*

- 10 sessions of tDCS stimulation over 2 weeks
- Bi-weekly sessions of tDCS stimulation over 3 weeks
- 4 Follow-Up Visits – 2 week, 4 weeks, 6 weeks, and 8 weeks post-stimulation

Eligibility criteria for Part II include:

- VAS pain score greater than 1 following either of the two SHAM stimulation sessions [97] during Part I and pain reduction not greater than 72.52% (i.e. not a large placebo response)
- Stable pain intensities (defined as a difference in pain intensities less than or equal to 4 (on a 0-10 VAS scale) between the average over the week prior to visit 2 and the average over the week prior to visit 4a [96])
- High adherence during the Run-in stimulation visits (defined as completing both Run-in stimulation visits within approximately one week)
- VAS pain weighted average  $\geq 3$  prior to randomization during visit 4a (i.e. not exhibiting low baseline pain)

**Detailed Study Outline**

Pre-screening Procedures:

During the pre-screening process, the subject will contact a co-investigator usually via a phone call. During this call, the co-investigator will discuss in greater depth the details of the study, explain the study procedures and encourage the subject to ask questions. In the privacy of the laboratory, the co-investigator will ask the subject questions from the following:

- 1) Phone screening questionnaire

Once this information is collected, the co-investigator will consult with the PI regarding the eligibility of the subject, who will then give approval for the subject to come to our laboratory for the screening procedure.

## **Part I – Run-in Period**

### **Visit 1**

Screening Visit – (Approx Time:  $\frac{3}{4}$  hour)

#### Screening Procedures:

At Screening, the PI and/or a co-investigator will once more conduct a review of inclusion/exclusion criteria to determine the subject's eligibility for enrollment. Study procedures will be reviewed with the subject, and documentation of informed consent will be obtained.

At Screening the following procedures will be completed:

- Discuss study-specific procedures with the subject.
- Review inclusion and exclusion criteria.
- Obtain a signed and dated consent form.
- Conduct a Demographics Survey and the Beck Depression Inventory.
- Urine pregnancy exam (if applicable).

This visit can be done remotely (There will be an electronically signed consent form, using Mass General Brigham REDCap eConsent and the visit will be done either by telephone or Zoom Healthcare)

### **Visit 2**

Baseline Testing/1st Run-in SHAM stimulation visit (Approx Time: 1  $\frac{1}{4}$  hours)

*The first baseline testing might be completed on the same day as the screening visit if time allows and the subject agrees.*

There will be 2 SHAM stimulation visits to be completed approximately 48 hours apart over about one week (this visit will include the first SHAM stimulation session). The subject will receive 20 minutes of SHAM tDCS in conjunction with SHAM TUS.

Before SHAM stimulation, the subject will complete the following assessments:

- Urine pregnancy exam (if applicable)
- Visual Analog Mood Scale (VAMS)
- Mini Mental State Examination (MMSE)
- Neurological and Physical Exam
- Visual Analogue Scale (VAS) for Pain
- Pain/Medication Diary
- EEG recording
- NIH CLBP RMD instrument
- 29-PROMIS short form
- Beck Depression Inventory (BDI)

After SHAM stimulation subjects will complete the following assessments:

- Adverse Events (AE)

- Visual Analogue Scale (VAS) for Pain
- Screening Form for Part II

### **Visit 3**

2nd Run-In SHAM Stimulation Visit/ End of Run-In Week – (Approx Time: ¾ hour)

Before SHAM stimulation, the subject will complete the following assessments:

- Visual Analogue Scale (VAS) for Pain
- Pain/Medication Diary
- 5 minute training session for motion tests to be performed during Part II

After stimulation subjects will complete the following assessments:

- Adverse Events (AE)
- Visual Analogue Scale (VAS) for Pain
- Screening Form for Part II

### **Visit 4a**

Rescreening Visit – (Approx Time: 1 ¼ hours)

*This study will be scheduled ~1 week after the first baseline measurements were done.*

The subject will complete a series of assessments:

- Urine pregnancy exam (if applicable)
- Visual Analog Mood Scale (VAMS)
- Mini Mental State Examination (MMSE)
- Stroop test
- Neurological and Physical Exam
- Visual Analogue Scale (VAS) for Pain
- Pain/Medication Diary
- Quantitative Sensory Testing (QST)
- Walking Test
- Postural Stability/Standing Test
- One Leg Stance Test
- Trunk Mobility Test
- Screening form for part II\*

\* If the subject is eligible for part II, then they will complete visit 4b in the same day.

Note, patients who exhibit large placebo effects (defined as exhibiting VAS=0 or VAS=1) following either of the two SHAM stimulation sessions[97] during Part I and score reduction higher than 72.52%; unstable pain intensities (defined as a difference in pain intensities larger than 4 (on a 0-10 VAS scale) between the average over the week prior to visit 2 and the average over the week prior to visit 4 [96]), low baseline pain (defined as weighted VAS avg < 3) prior to randomization during visit 4) or who are not compliant with the Run-In protocol (defined as not completing both Run-in stimulation visits within approximately one week) will be excluded from the full trial [96-98], and thus will not receive MRIs and will not come for

additional visits. By following this Run-in strategy, we will maximize trial resources by excluding patients who demonstrate poor compliance and are less likely to complete the trial. More importantly, we will increase the likelihood that the effects we are measuring in the full trial are biological in nature and directly caused by the stimulation intervention [97, 98]. Note, a patient can be screened out in any of the visits prior to Visit 4b.

